8.1.3 Reporting period

Details of all AEs (except those listed above) will be documented and reported from the date of commencement of protocol defined treatment until 30 days after the administration of the last treatment.

8.1.4 Post study SUSARs

SAEs that are judged to be at least possible related to the IMP(s) and are unexpected must still be reported in an expedited manner irrespective of how long after IMP administration the reaction occurred.

8.2 Reporting Procedure

8.2.1 Site

8.2.1.1 Adverse Events

AEs should be reported on an AE Form (and where applicable on an SAE Form). An AE Form should be completed at each visit and returned to the Trials Office.

AEs will be reviewed using the CTCAE, version 4.0 (see Appendix 6). Any AEs experienced by the patient but not included in the CTCAE should be graded by an Investigator and recorded on the AE Form using a scale of (1) mild, (2) moderate or (3) severe.

For each sign/symptom, the highest grade observed since the last visit should be recorded.

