7.5.1 General dose modifications for toxicities

Dose reduction and discontinuation guidelines for haematologic and non-haematologic toxicities due to AZD2014 are shown in Table 2 and 3. Dose re-escalation is not permitted.

Table 2.	Dose modifications and discontinuation criteria for non-haematologic toxicities*

NCI CTCAE Toxicity Grade	Action
Grade 1, or 2	None
Grade 3 or 4 and/or clinically significant	
Expected manageable/reversible with dose reduction	Hold study drug until meets one of the criteria below:
Toxicity remains (despite dose interruption) grade 3 or 4 or is clinically significant > 14 days	Discontinue study drug
Toxicity lasts 14 days or less and resolves to grade 2 or less or is no longer clinically significant	Reduce dose level per Table 1 and restart once toxicity has resolved to grade 2 or less or is no longer clinically significant
Grade 3 or 4 and/or clinically significant	
Not expected to be manageable/reversible with dose reduction	Discontinue study drug
Recurrence of Grade 3	Reduce one more dose level is available (see table 1), or if not discontinue study drug. NB note option of continuous dosing schedule as mentioned in 7.5

 Table 2.
 Dose modifications and discontinuation criteria for non-haematologic toxicities*

NCI CTCAE Toxicity Grade Action	
Recurrence of Grade 3 cardiac event ^a	Discontinue study drug
Recurrence of Grade 4	Discontinue study drug

* If the below specific recommendations for stomatitis/oral mucositis, hyperglycaemia, ILD/pneumonitis, ECG-changes and rash disagree with table 2 please follow the below not recommendations not table 2.

	Table 3.	Dose modifications and discontinuation criteria for haematological toxicitie
--	----------	--

NCI CTCAE toxicity grade	Action
Thrombocytopenia	
Grade 1, 2 or 3 (without bleeding)	None
Grade 3 (with bleeding) or grade 4	Hold study drug until it meets one of the criteria below:
Toxicity remains (despite dose interruption) grade 3 (with on-going bleeding episodes) or 4 > 14 days	Discontinue study drug
Toxicity lasts 14 days or less and resolves to grade 2 or less	Reduce dose level per table 1 and restart once toxicity has resolved to grade 2 or less
Neutropenia (NB GCSF is permitted as per local p	olicy)
Grade 1, 2 or 3	None
Grade 4	Hold study drug until it meets one of the criteria below:
Toxicity remains (despite dose interruption and GCSF) grade 4 > 14 days	Discontinue study drug

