8.2.1.2 Serious Adverse Events

For more detailed instructions on SAE reporting refer to the SAE Form Completion Guidelines contained in section 4 of the Investigator Site File (ISF).

AEs defined as serious and which require reporting as an SAE (excluding events listed in Section 8.1 above) should be reported on an SAE Form. When completing the form, the Investigator will be asked to define the causality and the severity of the AE which should be documented using the CTCAE version 4.0.

On becoming aware that a patient has experienced an SAE, the Investigator (or delegate) must complete, date and sign an SAE Form. The form should be faxed together with a SAE Fax Cover Sheet to the Trials Office using one of the numbers listed below as soon as possible and no later than 24 hours after first becoming aware of the event:

To report an SAE, fax the SAE Form with an SAE Fax Cover Sheet to:

[name] or [name]

On receipt the Trials Office will allocate each SAE a unique reference number. This number will be transcribed onto the SAE Fax Cover Sheet which will then be faxed back to the site as proof of receipt. If confirmation of receipt is not received within 1 working day please contact the Trials Office. The SAE reference number should be quoted on all correspondence and follow-up reports regarding the SAE. The SAE Fax Cover Sheet completed by the Trials Office should be filed with the SAE Form in the ISF.

For SAE Forms completed by someone other than the Investigator the Investigator will be required to countersign the original SAE Form to confirm agreement with the causality and severity assessments. The form should then be returned to the Trials Office in the post and a copy kept in the ISF.

Investigators should also report SAEs to their own Trust in accordance with local practice.

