12.2 Analysis of Outcome Measures

- Best overall response will be reported as the number and proportion of patients in each response category, and overall, during the first 6 cycles of treatment. In addition, best response observed after 6 cycles until the end of the trial will be reported by category and overall.
- The number and proportion of patients experiencing toxicity, including haematological and nonhaematological toxicity, will be reported with 95% confidence intervals.
- Time to event outcomes will be assessed using the method of Kaplan and Meier with point estimates presented at 6, 12, 24 and 36 months with 95% confidence intervals along with median survival time and confidence intervals. A Kaplan meier plot will be produced.
- The mean maximum % decrease during the first 6 cycles of treatment and overall will be reported with 95% confidence intervals

The biomarker study and PET scan analysis at present are exploratory.

There is little data on the expression of mTOR pathway proteins in DLBCL so the aim is to define expression in biopsy samples taken at relapse (or within 3 months). In collaboration with AstraZeneca, we will assess the expression of these proteins (p-S6, p-AKT, and p-4E-BP1) by immunohistochemistry (IHC). These will be measured at relapse, at subsequent progression, and in any tissue obtained at further optimal biopsy at 15 days. This will be initially assessed in 8 patients, with the potential to expand the analysis dependent on response data. We will then seek to determine a cut off which best predicts response to AZD2014, if indeed there is any correlation. Appropriate

statistical models (e.g. area under the curve, logistic regression) will be used to determine the cut off as detailed in the Statistical Analysis Plan.

Other ethically approved research may be performed on these samples if agreed by the trial management group.

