APPENDIX 5- DEFINITION OF ADVERSE EVENTS

Adverse Event

Any untoward medical occurrence in a patient or clinical trial subject administered a medicinal product and which does not necessarily have a causal relationship with this treatment. Comment:

An AE can therefore be any unfavourable and unintended sign (including abnormal laboratory findings), symptom or disease temporally associated with the use of an investigational medicinal product, whether or not related to the investigational medicinal product.

Please note this does not include abnormal laboratory findings. An abnormal laboratory value is only considered to be an AE if the abnormality:

- Results in early discontinuation from the study treatment and/or
- Requires study drug dose modification or interruption, any other therapeutic intervention, or is judged to be of significant clinical importance
- Is Hyperglycaemia of > 1 week or if the investigator considers the rise in glucose to be medically significant

If a laboratory abnormality is one component of a diagnosis or syndrome, then only the diagnosis or syndrome should be recorded.

Pre-existing events should only be classified as AEs if they worsen by at least one grade from screening.

Adverse Reaction

All untoward and unintended responses to an IMP related to any dose administered.

Comment:

An AE judged by either the reporting Investigator or Sponsor as having causal relationship to the IMP qualifies as an AR. The expression reasonable causal relationship means to convey in general that there is evidence or argument to suggest a causal relationship.

Serious Adverse Event

Any untoward medical occurrence or effect that at any dose:

- Results in death
- Is life-threatening*
- Requires hospitalisation** or prolongation of existing inpatients' hospitalisation
- Results in persistent or significant disability or incapacity
- Is a congenital anomaly/birth defect
- Or is otherwise considered medically significant by the Investigator***

Comments:

The term severe is often used to describe the intensity (severity) of a specific event. This is not the same as serious, which is based on patients/event outcome or action criteria.

* Life threatening in the definition of an SAE refers to an event in which the patient was at risk of death at the time of the event; it does not refer to an event that hypothetically might have caused death if it were more severe.

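### The AE Form scale for events not in CTCAE stops at severe, which conflicts with the CTCAE grading required elsewhere and does not map onto Table 2

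*Protocol*

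**What the plan says.** Protocol section 8.2.1.1 sets the general rule: "AEs will be reviewed using the CTCAE, version 4.0 (see Appendix 6"). It then makes an exception for events that CTCAE does not include, which "should be graded by an Investigator and recorded on the AE Form using a scale of (1) mild, (2) moderate or (3) severe". The same section asks for the worst grade since the previous visit and sends a serious event to the SAE Form as well as the AE Form.

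For the SAE Form, section 8.2.1.2 asks the Investigator to "define the causality and the severity of the AE which should be documented using the CTCAE version 4.0". It makes no exception for terms that CTCAE lacks. Section 12.1.2 bases tolerability on toxicities recorded with CTCAE v4.0, and Appendix 6 says the same of toxicities in general. Neither mentions a three-level scale.

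Table 2 in section 7.5.1 is indexed by NCI CTCAE grade. Its recurrence rows include one for Grade 3 and a separate one headed "Recurrence of Grade 4".

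**The concern.** A scale that ends at severe cannot describe an event that threatened life or caused death. On the AE Form, such an unlisted event can be graded no higher than 3. On the SAE Form, the same event has to be graded by CTCAE. The protocol neither requires the two grades to agree nor says which one enters the toxicity analysis.

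Toxicity is a secondary outcome in both stages, and section 1.2.3 presents the drug as a new therapeutic class with no efficacy data in this disease. If a table separated grade 4 or grade 5 and drew on AE Forms, unlisted events could not appear in those rows. An unlisted event coded on the three-level scale also has no route to the Grade 4 recurrence row of Table 2.

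**Working it through.** The protocol gives no figure on this point, so the main check sets the passages side by side. One assumption is needed because CTCAE is not reproduced in the protocol: grade 4 is taken as life-threatening and grade 5 as fatal.

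**Step 1. The rules that meet on one unlisted serious event.**

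| Place in the Protocol | Scale | Exception for unlisted terms |
|---|---|---|
| 8.2.1.1, AE Form | mild, moderate, severe (1 to 3) | this is the exception |
| 8.2.1.2, SAE Form | CTCAE v4.0 | none stated |
| 12.1.2, tolerability outcome | CTCAE v4.0 | none stated |
| Appendix 6 | CTCAE v4.0 | none stated |
| 7.5.1, Table 2 | CTCAE grade, with 3 and 4 separated on recurrence | none stated |

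**Step 2. Follow one event.** Appendix 5 defines an SAE by criteria that include "Results in death" and "Is life-threatening". An unlisted event of either kind therefore goes on both forms. The AE Form rule gives it 3. The SAE Form rule asks for a CTCAE grade for a term that CTCAE does not contain. The two rules conflict on the very events that need the missing levels.

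**Step 3. Which counts can change.** Write g for the grade on five levels and min(g, 3) for what the AE Form records.

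- Grade 3 or higher: g ≥ 3 holds exactly when min(g, 3) ≥ 3, so this count is unchanged.
- Grade 4 or higher: min(g, 3) ≥ 4 never holds, so unlisted events contribute nothing to this count if it is taken from AE Forms.
- Any toxicity: unchanged.

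Section 12.2 plans this: "The number and proportion of patients experiencing toxicity, including haematological and nonhaematological toxicity, will be reported with 95% confidence intervals". It names no grade 4 or grade 5 summary.

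**Step 4. The decision rules.** Section 12.6 counts toxicities that lead to treatment delay or dose modification in the first two cycles. Let X₁ and X₂ be the tolerable outcomes in the first and second 15 patients, each binomial(15, p).

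- Chance of stopping at 15 patients: P(X₁ ≤ 9). At p = 0.60 this is 59.7% (protocol 59.7%).
- Chance of concluding tolerable: the sum over x = 10 to 15 of P(X₁ = x) × P(X₂ ≥ 21 − x). At p = 0.60 this is 15.2% (protocol 15.3%). At p = 0.80 it is 90.5% (protocol 90.4%).

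The plan's figures reproduce to within 0.1 percentage point, and grade is not an input to any of them. The combination-stage rules (2 of 3, then 4 of 6) use the same outcome. At first occurrence, Table 2 puts Grades 3 and 4 in the same rows, so the cap makes no difference there. A recurrence follows a first event that has already been acted on.

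**Step 5. Size.** The documents give no expected number of unlisted grade 4 or 5 events. For illustration only, one such event among the 6 combination patients would be 1/6 = 16.7% against 0/6 = 0% if read from AE Forms. Among the 30 monotherapy patients it would be 1/30 = 3.3% against 0%.

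**The case against.** A reader might infer that grade 4 and 5 toxicity is under-reported in this trial. The documents do not support that. A fatal or life-threatening event is an SAE by definition, and section 8.2.1.2 requires the form within 24 hours with a CTCAE severity. A Clinical Coordinator assesses seriousness and causality independently (8.2.2), and the Trial Safety Committee reviews all SAEs (8.2.5). No analysis in the protocol is stated as a grade 4 or 5 rate. Which form feeds a table is properly a matter for the SAP, which is not at hand. The 16.7% against 0% contrast supposes both an event and a table that the protocol does not mention.

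A reader might also infer that the cap changes how patients are managed. That is not shown either. Table 2 is indexed by CTCAE grade, and nothing says that the three-level code is read into it. Its first-occurrence rows also cover any clinically significant toxicity. Sections 7.5 and 7.9 leave room for the physician's judgement.

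Two further points stand in part. The set of life-threatening or fatal events that CTCAE v4.0 leaves without a term may be very small or empty, and the documents cannot settle this. The SAE completion guidelines in the site file, which were not available, may say how to grade an unlisted term.

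None of this removes the conflict in the text. SAE reporting protects oversight of the individual case. It does not fix the grade held in the AE data, and Appendix 5 itself warns that severity and seriousness are different things.

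**Conclusion.** The point holds as an inconsistency with a limited effect. Followed as written, section 8.2.1.1 cannot express life-threatening or fatal severity for an unlisted event. It disagrees with sections 8.2.1.2 and 12.1.2 and Appendix 6, and it does not map onto the recurrence rows of Table 2.

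The events themselves are still captured as SAEs. The interim and final tolerability rules, their error rates and any count of grade 3 or higher are unaffected. What could be too low is a separate count of grade 4 or grade 5 taken from AE Forms. The shortfall would equal the number of patients whose only event at that level is an unlisted one. That number is not given and is probably small.

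The conclusion assumes the usual meaning of CTCAE grades 4 and 5, and that no document outside the protocol already settles which grade governs.

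**What to change.** - In section 8.2.1.1, extend the scale for unlisted events to five levels by adding 4 (life-threatening) and 5 (fatal).
- Require the same grade on the AE Form and the SAE Form, or state that the SAE Form grade governs the analysis.
- Check unlisted events already graded 3 on AE Forms against the SAE records and correct the grade where needed.
- Reconcile section 8.2.1.1 with Table 2, so that it is clear how an unlisted event is placed in the table. Which dose action belongs to which row is a clinical matter on which this point takes no position.

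The cost is low: a sentence or two of protocol text, two extra options on a form and a short data check. Section 9.1 lets the Trials Office change forms without a protocol amendment, and the text change can go into the next amendment. Sample size and decision rules stay as they are.

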8.2.1.2 Serious Adverse Events

For more detailed instructions on SAE reporting refer to the SAE Form Completion Guidelines contained in section 4 of the Investigator Site File (ISF).

AEs defined as serious and which require reporting as an SAE (excluding events listed in Section 8.1 above) should be reported on an SAE Form. When completing the form, the Investigator will be asked to define the causality and the severity of the AE which should be documented using the CTCAE version 4.0.

On becoming aware that a patient has experienced an SAE, the Investigator (or delegate) must complete, date and sign an SAE Form. The form should be faxed together with a SAE Fax Cover Sheet to the Trials Office using one of the numbers listed below as soon as possible and no later than 24 hours after first becoming aware of the event:

To report an SAE, fax the SAE Form with an SAE Fax Cover Sheet to:

[name] or [name]

On receipt the Trials Office will allocate each SAE a unique reference number. This number will be transcribed onto the SAE Fax Cover Sheet which will then be faxed back to the site as proof of receipt. If confirmation of receipt is not received within 1 working day please contact the Trials Office. The SAE reference number should be quoted on all correspondence and follow-up reports regarding the SAE. The SAE Fax Cover Sheet completed by the Trials Office should be filed with the SAE Form in the ISF.

For SAE Forms completed by someone other than the Investigator the Investigator will be required to countersign the original SAE Form to confirm agreement with the causality and severity assessments. The form should then be returned to the Trials Office in the post and a copy kept in the ISF.

Investigators should also report SAEs to their own Trust in accordance with local practice.

8.2.1.3 Provision of follow-up information

Patients should be followed up until resolution or stabilisation of the event. Follow-up information should be provided on a new SAE Form (refer to the SAE Form Completion Guidelines for further information).

8.2.2 Trials Office

On receipt of an SAE Form seriousness and causality will be determined independently by a Clinical Coordinator. An SAE judged by the Investigator or Clinical Coordinator to have a reasonable causal relationship with the trial medication will be regarded as a Serious Adverse Reaction (SAR). The Clinical Coordinator will also assess all SARs for expectedness. If the event meets the definition of a SAR that is unexpected (i.e. is not defined in the RSI/ Investigator Brochure) it will be classified as a Suspected Unexpected Serious Adverse Reaction (SUSAR).

8.2.3 Reporting to the Competent Authority and main Research Ethics Committee

8.2.3.1 Suspected Unexpected Serious Adverse Reactions

The Trials Office will report a minimal data set of all individual events categorised as a fatal or life threatening SUSAR to the Medicines and Healthcare products Regulatory Agency (MHRA) and main Research Ethics Committee (REC) within 7 days. Detailed follow-up information will be provided within an additional 8 days. All other events categorised as SUSARs will be reported within 15 days.

8.2.3.2 Serious Adverse Reactions

The Trials Office will report details of all SARs (including SUSARs) to the MHRA and main REC annually from the date of the Clinical Trial Authorisation, in the form of an Annual Safety Report.

8.2.3.3 Adverse Events

Details of all AEs will be reported to the MHRA on request.

8.2.3.4 Other safety issues identified during the course of the trial

The MHRA and main REC will be notified immediately if a significant safety issue is identified during the course of the trial.

8.2.4 Investigators

Details of all SUSARs and any other safety issue which arises during the course of the trial will be reported to Principal Investigators. A copy of any such correspondence should be filed in the ISF.

8.2.5 Safety Monitoring Committee

The Trial Safety Committee (TSC) will review all SAEs.

8.2.6 Manufacturer of Investigational Medicinal Product

All SAEs will be reported to the manufacturers of the Investigational Medicinal Products as defined in the agreement between sponsor and manufacturer. All SAEs will be reported to AstraZeneca in accordance with the Drug Supply Agreement.

9. DATA HANDLING AND RECORD KEEPING

9.1 Data Collection

The Case Report Form (CRF) will comprise a set of forms capturing details of eligibility, patient baseline characteristics, treatment and outcome details etc, and will be provided to the Site at the time of initiation.

The CRF must be completed, signed/dated and returned to the Trials Office by the Investigator or an authorised member of the site research team (as delegated on the Site Signature and Delegation Log) within stipulated timeframes. The exceptions to this are the SAE Form, eligibility Form and Withdrawal Form which must be signed by the Investigator.

Entries on the CRF should be made in ballpoint pen, in blue or black ink, and must be legible. Any errors should be crossed out with a single stroke, the correction inserted and the change initialled and dated. If it is not obvious why a change has been made, an explanation should be written next to the change.

Data reported on each form should be consistent with the source data or the discrepancies should be explained. If information is not known, this must be clearly indicated on the form. All missing and ambiguous data will be queried. All sections are to be completed before returning.

In all cases it remains the responsibility of the Investigator to ensure that the CRF has been completed correctly and that the data are accurate.

The completed originals should be sent to the Trials Office and a copy filed in the Investigator Site File.

Trial forms may be amended by the Trials Office, as appropriate, throughout the duration of the trial. Whilst this will not constitute a protocol amendment, new versions of the form must be implemented by participating sites immediately on receipt.

9.2 Archiving

It is the responsibility of the Principal Investigator to ensure all essential trial documentation and source records (e.g. signed ICFs, Investigator Site Files, Pharmacy Files, patients' hospital notes, copies of CRFs etc.) at their site are securely retained for at least 25 years after the end of the trial. Do not destroy any documents without prior approval from the CRCTU Document Storage Manager.

